## **9.2 Statistical methods, sample size, and analyses**

### **9.2.1 Sample size**

The aim of the trial is to establish whether GSK and Baxter vaccines satisfy all three CPMP criteria, and if so compare them in terms of immunogenicity (for each vaccine/age group and each vaccine type). The sample size is in line with standard practice. The protocols for seasonal EU vaccine clinical trials and the criteria for assessment have been standardised within the EU. They stipulate that trials should be done with groups of at least 50 subjects. We will recruit 60 per group, allowing for up to 17% dropout. This will enable for example the trial to detect a 10% to 20% difference in seroprotection and seroconversion rates at the 5% significance level with 80% power.

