## 6.0 OVERALL STUDY DESIGN

### 6.1 Overall study design

This observer-blind, multi-centre study will be performed at three study sites in England (Leicester, Nottingham, and Sheffield) in a study population of healthy male and female adults, or adults with stable chronic medical conditions. Six groups of 60 male and female adults will be stratified by age (18-44, 45-64, and 65 years and older):

Age	1st Vaccination Day 0	2 nd Vaccination Day 21	Subjects/ group	Antibody measurements
18-44	GSK vaccine	GSK vaccine	60	Immunogenicity endpoints: Days 0, 21, & 42  Antibody kinetics: Days 7, 14, 28, 35  Antibody persistence: 6 months  Breadth of antibody response (if applicable) Days 0, 21 for immunogenicity endpoints & Days 7, 14, 28 & 35 for kinetics
	Baxter vaccine	Baxter vaccine	60	
45-64	GSK vaccine	GSK vaccine	60	
	Baxter vaccine	Baxter vaccine	60	
≥65	GSK vaccine	GSK vaccine	60	
	Baxter vaccine	Baxter vaccine	60	

At least 360 subjects will be randomly allocated to receive two 7.5µg HA doses of cell culture plain (i.e., non-adjuvanted) whole virus A/California/2009 (H1N1) vaccine, or two doses of AS03-adjuvanted influenza A/California/2009 (H1N1) split virus vaccine containing 3.75µg HA by IM injection. A second dose of the same vaccine containing the same quantity of antigen as in the first dose will be administered by the same route 21 days later. Subjects will be observed for local and systemic reactions for 30 minutes after each immunisation and will be monitored for any reactions and other adverse events for 7 days after each immunisation.

Blood for immunogenicity studies will be obtained at day 0 (pre-immunisation), day 7 ( $\pm 1$  day), day 14 ( $\pm 2$  days), day 21 ( $\pm 2$  days), day 28 ( $\pm 2$  days), day 35 ( $\pm 3$  days), day 42 ( $\pm 3$  days) and day 180 ( $\pm 10$  days).

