### **A. BOTH VACCINES ARRIVE AT EACH CENTRE PRIOR TO REGULATORY APPROVAL**

We will use a block randomisation scheme to ensure that balance between vaccines is maintained and all volunteers are randomly allocated to groups. Subjects who meet the study admission criteria will be enrolled into the study and will be assigned a **5 digit subject number**:

The first digit identifies the study site (1 for Leicester; 2 for Nottingham; 3 for Sheffield).

The second digit reflects the age of the subjects on Day 0 (1 for 18-44; 5 for 45-64; and 9 for 65 years and older).

The following three digits identify the subject within the site and will be assigned sequentially, starting with 001 corresponding to the first subject enrolled within each age band.

Thus each centre will have three randomisation lists, each list corresponding to each age band.

Each centre will continue recruiting volunteers within an age band until the tally for the centres reaches a total of 120 subjects for that age band.

Volunteers in each age band will be randomised by a computer generated randomization code (1:1 proportions in block size(s) that will be determined by the statistician to ensure balance across groups). The randomisation code for each age band will be stored in individual, sequentially-numbered envelopes, specific for each centre, and will be opened by the nurse with responsibility for vaccine administration. The type of vaccine for administration will be printed on an adhesive label. The label will be peeled from its backing and entered into an appropriate space in the 'Vaccine Log', ensuring that the instruction and vaccine that is administered actually agree (See below).

Only one study nurse/doctor will be responsible for vaccine administration in each centre. This study nurse/doctor will be un-blinded with respect to the type of vaccine administered; he/she will play no

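### The stated 80% power for a 10% to 20% difference does not hold at about 50 evaluable per vaccine/age group; it roughly fits only the all-ages comparison

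*Protocol*

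**What the plan says.** Section 9.2.1 of the protocol gives the aim as establishing whether both vaccines meet the three licensing criteria and, if so, to "compare them in terms of immunogenicity (for each vaccine/age group and each vaccine type"). It justifies the group size by the EU convention: "They stipulate that trials should be done with groups of at least 50 subjects". It continues "We will recruit 60 per group, allowing for up to 17% dropout", and the next sentence says, as an example, that this lets the trial "detect a 10% to 20% difference in seroprotection and seroconversion rates at the 5% significance level with 80% power".

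Section 6.1 defines the groups: "Six groups of 60 male and female adults will be stratified by age (18-44, 45-64, and 65 years and older"). Allocation is equal, with "1:1 proportions in block size(s) that will be determined by the statistician to ensure balance across groups" (section 7.4, scenario A). Section 9.2.5.1 plans Pearson's chi-square or Fisher's exact test for the binary outcomes, without adjustment for multiple testing, and makes the between-vaccine comparison conditional on both vaccines meeting all three criteria.

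The power sentence states no underlying rate, no sidedness and no comparison level. The synopsis has the same sample-size paragraph without the power sentence.

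**The concern.** The power sentence follows directly from 60 per group less dropout, and the groups are vaccine-by-age cells. The natural reading is therefore that about 50 v 50 within an age band gives 80% power for differences of 10 to 20 points. Samples of that size seldom give such power for a difference of 10 points between two proportions.

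The age-band comparisons matter. The conclusions of section 4.0 ask whether one vaccine spares dose in older people and seroconverts more of the young, and section 9.2.7 says early results are to inform vaccination strategy. Someone relying on the printed figure could take a non-significant result in one age band as good evidence against a 10- to 20-point difference.

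**Working it through.** **Inputs from the protocol.** Significance level 5% and power 80% (9.2.1); 60 recruited per group with up to 17% dropout (9.2.1); equal allocation (7.4); three age bands per vaccine (6.1).

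**Assumptions.** Two-sided testing. Differences in absolute percentage points; a relative reading would make them smaller and the power lower. Underlying rates are varied because none is given.

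**Evaluable numbers.** 60 × 0.83 = 49.8, so about 50 per vaccine in an age band. This reproduces the EU minimum of 50. Over three bands, 3 × 50 = 150 per vaccine.

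**Formula.** With n per arm, rates p1 and p2, d = p1 − p2 and p̄ = (p1 + p2)/2:

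power = Φ{ [d − 1.96 √(2 p̄(1 − p̄)/n)] / √([p1(1 − p1) + p2(1 − p2)]/n) }

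*Example, 90% v 70%, n = 50.* p̄ = 0.80. The first root is √(0.32/50) = 0.0800, and 1.96 × 0.0800 = 0.1568. The second root is √(0.30/50) = 0.0775. Power = Φ(0.0432/0.0775) = Φ(0.558) = 71%.

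*Example, 90% v 80%, n = 50.* p̄ = 0.85. The roots are 0.0714 and 0.0707. Power = Φ((0.10 − 0.1400)/0.0707) = Φ(−0.565) = 29%.

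**Power at 50 v 50** (exact values by full enumeration; a dash means not computed):

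| Rates | Normal approx. | Exact chi-square | Fisher's exact |
|---|---|---|---|
| 100 v 90 | 63% | 75% | 38% |
| 95 v 85 | 38% | 39% | 24% |
| 90 v 80 | 29% | – | – |
| 80 v 70 | 21% | – | – |
| 95 v 75 | 81% | 85% | 75% |
| 90 v 70 | 71% | 73% | 64% |
| 80 v 60 | 59% | 60% | 52% |
| 70 v 50 | 53% | 55% | 46% |

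The formula is symmetric, so 25 v 5 has the same 81% as 95 v 75. The stated 80% is not reproduced at the 10-point end for any rate. At the 20-point end it is reproduced only when the higher rate is about 95% or more, or the lower rate about 5% or less.

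**Smallest difference with 80% power, in points** (same formula solved for d):

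| Higher rate | 50 v 50 | 150 v 150 |
|---|---|---|
| 100% | 14 | 5 |
| 95% | 20 | 10 |
| 90% | 23 | 12 |
| 80% | 26 | 14 |
| 60% | 28 | 16 |

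Apart from rates near 100%, the 150 v 150 column lies roughly within the stated 10 to 20. Even there, 10 points needs a higher rate of about 94% or more: power is 83% for 95 v 85, but 68% for 90 v 80 and 52% for 80 v 70.

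**Sample size for 10 points.** Evaluable numbers per arm are 74 (100 v 90), 141 (95 v 85), 199 (90 v 80), 294 (80 v 70) and 388 (60 v 50).

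**Variants.** With no dropout (60 v 60), the normal approximation gives at most 72% for 10 points, 79% for 90 v 70 and 67% for 80 v 60. With a one-sided 5% test at 50 v 50, 10 points has at most 75% by normal approximation.

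**The case against.** **The sentence may mean the pooled comparison.** It speaks of the trial, is offered as an example, and follows an aim that names both levels. At 150 v 150 the range roughly fits. This stands as a possible origin of the figure. But section 9.2.1 gives no pooled sample size, ties the figure to 60 per group and names the age-group comparison as an aim, so the claim is not limited to pooled data.

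**Favourable conditions exist.** Dropout of 17% is a maximum; with all 60 evaluable, 90 v 70 has 80% power by exact chi-square. Sidedness is unstated; a one-sided exact chi-square at 50 v 50 gives 89% for 100 v 90. For 10 points the escape is narrow: with 60 v 60 two-sided, exact chi-square power is 86% at 100 v 90 but 70% at 99 v 89, and with 50 v 50 one-sided it is 78% at 99 v 89. So 10 points is rescued only with one arm at or almost at 100%.

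**The comparison is conditional.** Both vaccines must first meet all three criteria. With 50 subjects and a true seroprotection rate of 50%, the chance of observing more than 70% is about 0.1%; with a true rate of 60% it is about 5%. Pairs such as 70 v 50, and in adults 80 v 60, would therefore seldom be tested for seroprotection. This stands. Those pairs matter mainly for seroconversion, where the thresholds are 40% and 30%. It does not help the 10-point end.

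**Stronger readings a reader might infer.** One is that the trial is too small for its main purpose. The protocol does not support this: group size rests on the EU convention, and the primary objective is assessment against licensing criteria, which does not use this figure. Another is that 20-point differences would usually be missed; power of 53% to 71% does not bear that out. Nor does the protocol claim equivalence or non-inferiority; the risk lies in how a non-significant age-band result is read.

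**Conclusion.** The power statement is wrong for the comparison to which its paragraph attaches it. At the planned evaluable size within an age band, the 10-point end fails at every rate (two-sided 5%), with power of 21% to 38% when the higher rate is 80% to 95%. The 20-point end holds only at extreme rates. The detectable difference there is about 14 to 28 points, against about 10 to 16 for all ages with higher rates of 95% down to 60%.

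This rests on two-sided testing, absolute differences, about 17% dropout and assumed rates. Fisher's exact test would make the age-band figures worse. The consequence is confined to between-vaccine comparisons of seroprotection and seroconversion within age bands.

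**What to change.** Replace the power sentence in section 9.2.1 with one that names the comparison level and sidedness and labels the rates as assumptions. For example:

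*Assuming 50 evaluable subjects per vaccine in an age group and a two-sided 5% test, there is 80% power for a difference of about 14 percentage points if the higher rate is near 100%, 20 if it is 95%, 23 if 90%, and 26 to 28 if 60% to 80%. With 150 per vaccine (all ages) the corresponding differences are about 10 points if the higher rate is 95%, 12 if 90%, and 14 to 16 if 60% to 80%.*

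Limit the 10-point end of the claim to the all-ages comparison. If Fisher's exact test is likely to be used in the age bands, say that power will be somewhat lower.

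The cost is one paragraph and a less favourable figure for the age bands. The planned tests in section 9.2.5.1, the sample size and the primary assessment stay as they are.

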### **9.2.2 Definition of populations to be analysed**

Definition of populations to be analyzed:

#### *(a) All enrolled population*

- All subjects in the enrolled population

#### *(b) Full analysis set, Immunogenicity*

- All subjects in the enrolled population who:
  - actually receive at least one dose of study vaccination, and
  - provide at least one evaluable serum sample both before and after baseline

#### *(c) Per protocol (PP) population, Immunogenicity*

- All subjects in the enrolled population who:

- receive all the relevant doses of vaccine correctly, and
- provide evaluable serum samples at the relevant time points, and
- have no major protocol violation as defined prior to statistical analysis

A major deviation is defined as a protocol deviation that is considered to have a significant impact on the immunogenicity result of the subject.

*(d) Adverse events population*

- All subjects who received at least one dose of the study vaccine who:
  - Provide post-baseline adverse events data

**9.2.3 Analysis of demographic and baseline characteristics**

Descriptive statistics (mean, standard deviation, median, minimum, and maximum) for age, together with distributions of subjects by sex and ethnic origin, previous influenza vaccination (during the past three seasons), recent influenza-like illness in the patient (since May 2009), and presence of pre-vaccination antibody to the vaccine strain will be summarized overall, for each vaccine group, and by age group.

**9.2.4 Analysis of immunogenicity criteria**

Blood samples for immunogenicity assays will be collected on Days 0 (prevaccination), 7, 14, 21, 28, 35, 42, and 180.

Antibody response will be evaluated by haemagglutination inhibition (HI), neutralization (MN), and possibly single-radial haemolysis (SRH) in all subjects.

HI and/or MN antibody titres need to be assessed rapidly and so will be analysed in three tranches:

- 1st tranche of sera measuring antibodies before and after 1st injection: Days 0, 7, 14, and 21
- 2nd tranche of sera measuring antibodies before and after 2nd injection: Days 21, 28, 35, and 42.
- 3rd tranche of sera measuring persistence of antibodies: Days 0, 42 and 180.

HI and MN assays will be performed at the Health Protection Agency Centre for Infections, Enteric, Respiratory & Neurological Virus Laboratory, London, UK. SRH tests may be done at the National Institute for Biological Standards and Control. Antibody titrations will be done in duplicate. Pre- and post-vaccination samples from each person will be titrated simultaneously, as specified in the CHMP guidance. The titre assigned will be the geometric mean of two independent determinations.

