**9.2.5 Immunogenicity objectives**

**9.2.5.1 Primary immunogenicity objective**

The primary immunogenicity objective is to evaluate the immunogenicity of Baxter cell-culture, non-adjuvanted, whole virus H1N1 vaccine, and GSK AS03-adjuvanted, split H1N1 vaccine with respect to Committee of Human Medicinal Products (CHMP) and FDA licensing criteria.

These criteria for adults aged between 18 and 60 years are, for sera collected ‘approximately 3 weeks after vaccination’:

- Number of seroconversions or significant increase in antihaemagglutinin antibody titres >40%
- Mean geometric increase >2.5
- The proportion of subjects achieving an HI titre of  $\geq 40$  or SRH titre of  $25 \text{ mm}^2$  should be >70%

For adults aged over 60 years these criteria are:

- Number of seroconversions or significant increase in antihaemagglutinin antibody titres >30%
- Mean geometric increase >2.0
- The proportion of subjects achieving an HI titre of  $\geq 40$  or SRH titre of  $25 \text{ mm}^2$  should be >60%

The measures of immunogenicity will be calculated as:

*Geometric Mean Titre or Geometric Mean Area:* For each vaccine/age group and each vaccine type, least squares GMTs for HI and MN data (GMAs for SRH data), associated 95% confidence interval and median, minimal, and maximal titre value will be determined for each visit, i.e., days 0, 7, 14, 21, 28, 35, 42, and 180.

**Geometric Mean Ratio (increase):** For each vaccine/age group and each vaccine type, the least squares GMRs will be calculated for the HI, MN and SRH results for the following time points of the study: day 7/day 0, day 14/day 0, day 21/day 0, day 28/day 0, day 35/day 0, day 42/day 0, as well as the associated 95% confidence intervals and the median, minimal, and maximal n-fold increase. Statistical methods used to analyze GMRs will be identical to those described above for GMTs (GMAs).

**Seroconversions:** Percentages of subjects with seroconversion (or significant increase in HI titre). The number and proportion of subjects achieving seroconversion or significant increase in HI titres or SRH area from pre-immunization to each visit after first immunization will be tabulated for each vaccine/age group and each age group.

- Seroconversion is defined as negative pre-vaccination serum (<10 for HI, <4 for SRH) / positive post-vaccination titre ( $\geq 40$  for HI, area  $\geq 25 \text{ mm}^2$  for SRH).

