- Significant increase in antibody titre/area is defined as at least a fourfold increase in HI or a 50% increase in area from non-negative pre-vaccination serum ( $\geq 10$  for HI,  $\geq 4$  for SRH).

**Seroprotection:** Percentages of subjects achieving each of the following thresholds: inverse HI titre  $\geq 40$ , SRH area  $\geq 25 \text{ mm}^2$ : The number and proportion of subjects achieving each threshold at each visit will be tabulated for each vaccine/age group and each vaccine type.

All statistical analyses for HI and SRH will be performed on the logarithmically (base 10) transformed values. Titres below the limit of detection for assays will be set to 1 in 5 for HI and  $4 \text{ mm}^2$  for SRH for the purposes of analysis. Original values will be presented in all listings

The above immunogenicity criteria will be applied to sera collected 21 days after completion of vaccination, i.e., 21 days after the second vaccine dose. For pandemic vaccines, all three criteria should be met.

Should both GSK and Baxter vaccines satisfy all three CPMP criteria, we will compare the immunogenicity of the two vaccines (for each vaccine/age group and each vaccine type) in terms of:

- a. Geometric mean titres 21 days after each vaccination;
- b. Geometric mean ratio increases 21 days after each vaccination;
- c. Seroprotection rates 21 days after each vaccination;
- d. Seroconversion rates 21 days after each vaccination.

Comparisons will be made using parametric or non-parametric tests as appropriate for continuous outcomes, and Pearson's chi-square test or Fisher's exact test where appropriate for categorical outcomes. Further analyses using (generalised) linear models will explore the effect of baseline covariates on the outcomes. For populations (a) and (b), analyses using multiple imputation to allow for missing data will also be undertaken as a sensitivity analysis. No formal adjustment will be made for multiple testing but associated P-values will be interpreted cautiously.

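### The second assay tranche has no Day 0 serum, so Day 28, Day 35 and interim Day 42 rises over baseline cross tranches, against the protocol's own simultaneous-titration rule

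*Protocol*

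**What the plan says.** Section 9.2.4 splits the HI and MN work into three tranches so that results come quickly:

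- First: "injection: Days 0, 7, 14, and 21".
- Second: "injection: Days 21, 28, 35, and 42".
- Third: "tranche of sera measuring persistence of antibodies: Days 0, 42 and 180".

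It then sets the rule that "Pre- and post-vaccination samples from each person will be titrated simultaneously, as specified in the CHMP guidance".

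Section 9.2.5.1 fixes the baseline. Geometric mean ratios are to be calculated for "day 7/day 0, day 14/day 0, day 21/day 0, day 28/day 0, day 35/day 0, day 42/day 0", and seroconversion or significant increase "from pre-immunization to each visit after first immunization will be tabulated". On timing of the primary criteria: "The above immunogenicity criteria will be applied to sera collected 21 days after completion of vaccination, i.e., 21 days after the second vaccine dose". That is Day 42.

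Section 9.2.5.2(b) applies the licensing criteria 7 and 14 days after each dose, which for the second dose means Days 28 and 35. Section 9.2.7 lists the first two tranches, and not the third, for interim reporting to the Department of Health.

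**The concern.** Two of the three licensing criteria (the mean geometric increase and the seroconversion rate) compare a person's later titre with that person's Day 0 titre. Titrating the pair together removes a shift between assay runs, because the shift affects both titres. When the two are titrated on different occasions, any systematic shift enters the fold rise directly and is indistinguishable from a vaccine effect. Seroprotection uses the later titre alone and needs no pair.

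The second tranche is where Day 42 is first measured, and it is the tranche reported early to inform vaccination strategy. It contains no Day 0 serum. At stake are the interim Day 42 reading and the whole post-second-dose kinetics analysis.

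**Working it through.** **Step 1. Which visits share a tranche with Day 0?** Inputs are the three lists in section 9.2.4.

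| Visit | Tranche(s) | Tranche shared with Day 0 |
|---|---|---|
| Day 7 | 1 | 1 |
| Day 14 | 1 | 1 |
| Day 21 | 1, 2 | 1 |
| Day 28 | 2 | none |
| Day 35 | 2 | none |
| Day 42 | 2, 3 | 3 only |
| Day 180 | 3 | 3 |

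Days 28 and 35 cannot be paired with Day 0 within any tranche. Day 42 can be, but only in the third. The interim list stops at the second, so any Day 42/Day 0 rise at that stage uses Day 0 from tranche 1 and Day 42 from tranche 2. Days 0, 21 and 42 each have titres from two tranches, and the protocol does not say which Day 0/Day 42 pair decides the primary result. With Day 0 added to tranche 2, every visit would share a tranche with Day 0.

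**Step 2. How large could the effect be?** The protocol states no between-run figure for the laboratory, so the shift is an assumption. A systematic multiplicative shift f gives

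observed GMR = true GMR × f.

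Half a two-fold dilution is f = 0.71 or 1.41; a full dilution is f = 0.5 or 2.

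- At a true GMR of 2.5: 2.5 × 0.71 ≈ 1.8 and 2.5 × 1.41 ≈ 3.5 (half); 2.5 × 0.5 = 1.25 and 2.5 × 2 = 5.0 (full).
- The same arithmetic gives the range of true GMR in which a shift could move a group across its limit. For the limit of 2.5 (age 18 to 60): about 1.8 to 3.5 (half) or 1.25 to 5.0 (full). For the limit of 2.0 (over 60): 2.0/1.41 ≈ 1.4 to 2.0 × 1.41 ≈ 2.8 (half) or 1.0 to 4.0 (full). Outside these ranges the GMR verdict does not change.

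**Step 3. Share with at least a four-fold rise.** With a lognormal fold rise and an assumed SD of log10 fold rise,

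share = 1 − Φ((log10 4 − log10(GMR × f)) / SD).

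At a true GMR of 2.5:

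| SD (log10) | No shift | Half dilution, down to up | Full dilution, down to up |
|---|---|---|---|
| 0.4 | 31% | 19% to 45% | 10% to 60% |
| 0.6 | 37% | 28% to 46% | 20% to 56% |

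**Step 4. A limit on Step 3.** The four-fold rule in section 9.2.5.1 covers only subjects with a Day 0 HI titre of at least 10. A subject below 10 is set to 5 and must reach 40, a rise of 40/5 = 8-fold. For a mean rise of 1.0 log2 unit with SD 1.2 log2 units (both assumed) and upward shifts of 0, half and one dilution:

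- four-fold or more: 20.2%, 33.8%, 50.0%;
- eight-fold or more: 4.8%, 10.6%, 20.2%.

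The effect on the seroconversion rate therefore depends on the mix of baseline status, and the four-fold figures overstate it where many subjects are seronegative.

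**The case against.** **The third tranche pairs Days 0 and 42.** A reader might infer that the primary Day 42 fold rises and seroconversions must be read across runs. The protocol does not support that: a same-tranche pair is scheduled and is available for the final analysis. This objection stands in full for the final primary result. It does nothing for Days 28 and 35, or for the interim Day 42 reading.

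**Each tranche has its own pre-injection sample.** The second tranche is described as covering sera before and after the second injection, so Day 21 could be its pre-sample and the rule would be kept injection by injection. This softens the contradiction but does not remove it, because section 9.2.5.1 takes Day 0 as the baseline throughout. Day 21 could also serve as a bridge between the first two tranches, but none is described.

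**Choosing between two titres belongs in the analysis plan.** That is fair for the choice alone. Which sera are assayed together, however, is fixed in section 9.2.4, and an analysis plan cannot put a Day 0 serum into a run that did not contain it.

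**The size is assumed.** This stands. The 32-fold variability in section 4.0 is between laboratories, and one laboratory runs all HI and MN assays, so that figure cannot be carried over. Shifts that differ from run to run would partly average out in a group mean. All three criteria must also be met: at a true GMR of 2.0, a half-dilution shift lifts the GMR to 2.8, but the four-fold share of 34% (Step 4) still fails the 40% limit at age 18 to 60.

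**Early results are already called preliminary, and the vaccines are to be mixed.** Section 9.2.7 is headed as interim and preliminary, but it does not say that Day 42 rises would cross tranches. A reader might also infer a shift that differs between vaccines under sequential supply. Section 7.4 (scenario B) plans to try to include some second-vaccine sera in the first tranche, so a differential shift is possible but not established.

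**Conclusion.** The concern holds in a limited form. Independently of any assumption, the second tranche omits Day 0, so all Day 28/Day 0 and Day 35/Day 0 results and any interim Day 42/Day 0 result cross tranches, contrary to the simultaneous-titration rule in the same section. The final Day 42/Day 0 result need not cross tranches, but the protocol does not name the third-tranche pair as its source.

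The size is conditional. Under a systematic shift of half to one two-fold dilution, which is assumed, the GMR is multiplied or divided by 1.4 to 2. That matters for groups near the limits and not for groups well clear of them. This should be fixed, but it is not a fault that by itself invalidates the primary analysis.

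**What to change.** In section 9.2.4, change the second tranche to Days 0, 21, 28, 35 and 42, and state that each fold rise and seroconversion uses the Day 0 titre from the same run as the later sample. The cost is up to 360 further Day 0 titrations per assay (one per subject). Section 8.2 stores sera in triplicate. Day 0 would then be used in all three tranches, so a fourth Day 0 aliquot may be needed for SRH or a drift variant.

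If Day 0 serum is limiting, name the third-tranche Day 0/Day 42 pair as the source of the primary result, and report the interim Day 42 ratios and all Day 28 and Day 35 ratios as cross-run and preliminary. That costs only wording, but the final primary result waits for the Day 180 sera and the Day 28 and Day 35 ratios remain cross-run.
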